### **9.3. Study Drug Storage**

All SEP-363856 tablets are to be stored at controlled room temperature, between 15°C and 25°C (59°F and 77°F).

### **9.4. Dispensing of Study Drug**

Study drug will be administered on an in-patient basis as open-label 50 mg or 75 mg dosage strengths of SEP-363856. Subjects will take one tablet of study drug per day at approximately the same time each day with morning dosing recommended. Dosing may be moved to the evening for reasons of tolerability; except for the day of post dose fMRI scanning where dosing will occur approximately 2 to 4 hours before fMRI scanning. Study drug may be taken without regard to food.

Appropriate guidelines should be followed in proper dispensation to the study participant. Study drug will not be dispensed to any person who is not a study subject under this protocol.

### **9.5. Study Drug Accountability**

The Investigator or designee is responsible for maintaining adequate and up to date records of drug disposition that include the dates, quantities received and dispensed, and use by subjects.

Upon receipt of study drug, the Investigator or designee will inspect the supplies and confirm receipt of the shipment. The Investigator or designee will review the contents of each drug shipment against the provided packing list and confirm date of receipt, completeness of shipment and condition of study drug received.

### **9.6. Study Drug Handling and Disposal**

The Investigator or designee is responsible for storing the study drug in a secure location. Study drug should be maintained under the strict control of qualified site staff at all times. Proper storage and handling guidelines should be followed. An Investigational Product (IP) Manual will be supplied. In the event that study drug expires while at the site before it is returned to the depot, the Investigator or designee should store the expired study drug separately.

If the study is stopped for any reason or completed, all used and unused supplies of drug will be returned to the Sponsor, unless other instructions are provided in writing by Sponsor/contract research organization (CRO).

The Investigator or designee is required to return all unused study drug to the Sponsor or designee as instructed. The Investigator or designee is required to maintain copies of study drug shipping receipts, drug accountability records, and records of return of the study drug in accordance with local regulatory requirements.

## **10. TREATMENT OF SUBJECTS**

### **10.1. Study Medication**

All study drug doses will consist of tablet(s) containing SEP-363856 administered orally.

Subjects may take study drug with or without food. Study drug (Days 1 – 13) should be taken at approximately the same time each day with morning dosing recommended. Dosing may be moved to the evening for reasons of tolerability; except for the day of post dose fMRI scanning where dosing will occur approximately 2 to 4 hours before fMRI scanning.

#### **10.1.1. Dose Adjustment Criteria**

Subjects will receive SEP-363856 50 mg/day on Day 1 through Day 3. On Day 4, subjects will titrate up to a dose of 75 mg/day. Subjects may dose reduce one time to 50 mg/day for tolerability reasons at any time. Subjects who have a dose reduction for tolerability will continue to receive the reduced dose for the remainder of the study.

### **10.2. Treatment Compliance**

Study drug will be administered in-clinic. The Investigator will record the dose of the study drug and the dates of the initial and final administration for each dose.

### **10.3. Concomitant Medications and Therapies**

The following information on all medication administered between screening and end of study or at discontinuation will be recorded on the case report form (CRF): Medication name, dose, frequency, route, start date, stop date, and indication.

Prior treatment with antipsychotic agents including depot neuroleptics will be recorded for at least 6 months prior to the screening visit. All other prior treatments will be recorded for at least 3 months prior to screening.

Information on the format and version of coding dictionary is provided in the Data Management Plan (DMP). All medications will be coded using World Health Organization – Drug Dictionary (WHO-DD).

Subjects who require treatment with a prohibited concomitant medication will be discontinued from the study.

#### **10.3.1. Prohibited Medications**

Concomitant use of CYP2D6 inhibitors is prohibited as SEP-363856 is a potential substrate for CYP2D6.

All psychotropic medications and herbal supplements (with the exception of the single, background antipsychotic, or medications listed in [Section 10.3.4](#)) are prohibited during the study and must be discontinued, as tolerated and clinically appropriate (for at least 5 half-lives or 14 days, whichever is longer), prior to the first dose of study drug in a manner that is consistent with labeling recommendations and conventional medical practice.

Clozapine is prohibited. Prior exposure to clozapine is allowed, as long as treatment is discontinued at least 120 days prior to PET scan at screening.

Subjects who require treatment with one or more of the prohibited concomitant medications (including antidepressants, mood stabilizers, or anxiolytics [lorazepam or equivalent at doses above protocol-specified limits]) will be discontinued (as appropriate) from the study.

All efforts will be made to complete the PET and resting state fMRI scans intended by the protocol even in cases of discontinuations of study drug or procedures.

The majority of participants will receive up to 2 PET scans. Participants will only receive 3 PET scans in the event that a scan is not able to be completed or is not suitable for analysis.

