#### **Screening Period (up to 49 days):**

Informed consent will be obtained from each subject before any study procedures are performed. No imaging procedures involving ionizing radiation will be performed within 12 hours of written consent. Screening procedures will occur over multiple days. Subjects must be on a stable dose of a single antipsychotic medication, dose within the labeled dose-range, for a minimum of 3 weeks or if above the maximum label dose (country specific) for at least 12 weeks prior to the PET scan at the screening visit, and the dose should remain fixed throughout the study. Subjects who meet entry criteria may be in-clinic for up to 7 days during the screening period, at the Investigator's discretion.

During the screening period, those subjects who are outpatients will report to the imaging center for their PET scan at screening (~2 hours duration) and those subjects who are in-clinic will be transferred to the imaging center accompanied by clinic personnel. The PET scan will be performed prior to dosing (Day -44 to Day -2), with administration of F-DOPA occurring at the start of the PET scan session.

The screening MRI must occur prior to the PET scan at screening (Day -44 to Day -2). Prior to the PET scan at screening, a blood sample will be taken to determine antipsychotic plasma concentrations.

Subjects who are not already in-clinic will check into the clinic on Day -2.

Subjects who screen fail may be re-screened up to two times, if judged appropriate by the Investigator. Subjects who screen fail due to MRI or PET scan at screening or fMRI results may not be re-screened.

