**Prior Medications:**

Subjects must be on a stable dose of a single antipsychotic medication, dose within the labeled dose-range, for a minimum of 3 weeks or if above the maximum label dose (country specific) for at least 12 weeks prior to the PET scan at the screening visit, and the dose should remain fixed throughout the study. Depot neuroleptic dose must be stable for at least 2 treatment cycles or at least 30 days (whichever is longer) prior to the screening visit.

Prior exposure to clozapine is allowed, as long as treatment is discontinued at least 120 days prior to PET scan at screening. All other psychotropic medication (with the exception of the single background antipsychotic, or medications listed below), must be discontinued, as tolerated and clinically appropriate, prior to PET scan at screening in a manner that is consistent with labeling recommendations and conventional medical practice.

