## 7. INVESTIGATIONAL PLAN

### 7.1. Overall Study Design

This is a single-site, open-label, flexibly dosed study evaluating the effect on brain dopamine synthesis capacity as measured by F-DOPA PET imaging of adjunctive open-label administration with SEP-363856 (50 to 75 mg/day) over 2 weeks in adults with schizophrenia.

The study will consist of 3 periods: Screening (up to 49 days), Treatment (2 weeks), and a Follow-up visit as shown in Figure 1.

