25. Subject has used disallowed prescription or disallowed nonprescription drugs, or dietary or herbal supplements as specified within the Concomitant Medications and Restrictions ([Section 10.3](#)) for at least 5 half-lives or 14 days prior to dosing, whichever is longer, or

anticipates the need for any disallowed medication during their participation in this study (exception: female subjects who are taking oral, patch, or intrauterine device [IUD] hormonal contraceptives, or progestin implant or injection). Further details to be provided in [Section 10.3](#).

26. Subject is a staff member or the relative of a staff member.
27. Subject is in the opinion of the Investigator, unsuitable in any other way to participate in this study.
28. Subject has contraindications to undergoing MRI/fMRI examination including, but not limited to claustrophobia, metal foreign bodies or implanted devices incompatible with the MRI/fMRI exposure.

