### **10.3.2. Prohibited Therapies**

Electroconvulsive therapy (ECT) is prohibited within 3 months prior to screening and during the study.

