### **12.** PRIOR AND CONCOMITENT MEDICATIONS

Subjects may not take any disallowed prescription or disallowed non-prescription medications, or dietary or herbal supplements, for at least 5 half-lives or 14 days prior to dosing, whichever is longer or anticipate the need for any disallowed medication during their participation in this trial. Concomitant use of CYP2D6 inhibitors is prohibited. Subjects may not use Clozapine for at least 120 days prior to PET scan at screening. Antidepressants, mood stabilizers, or anxiolytics [lorazepam or equivalent at doses above protocol-specified limits] are prohibited concomitant medications. Electroconvulsive therapy is prohibited within 3 months prior to screening and during the study.

Other than the study drug, any medication taken during the course of the study, with a start date/time on or after the first dose of study drug and on or before the last dose of study drug; or with a start date/time prior to, and an end date/time on or after, the first dose of study drug, or marked as ongoing, will be considered concomitant. Medications that stopped prior to the first dose of study drug will not be considered concomitant but prior medications. Post treatment medications are medications which started after the last dose of study drug.

Antipsychotic agents including depot neuroleptics taken within at least 6 months prior to screening, and any other medications taken within at least 3 months prior to screening, through the End of Study visit will be recorded and reported. All medications will be provided in a listing for all subjects enrolled.

All medications will be coded using the World Health Organization Drug Dictionary (WHODRUG version 01MAR2019). The number and percentage of subjects using each prior/concomitant medication will be summarized for safety population for SEP-363856 (Overall) according to the WHODRUG Anatomic Therapeutic Class (ATC) Level III and preferred name. Subjects with multiple uses of a prior/concomitant medication will be counted once for a given ATC class and preferred name.

Similarly, the number and percentage of subjects using background antipsychotics, including typical, atypical, oral and depot antipsychotics, will be summarized for safety population for SEP-363756 (Overall) according to the

Document:	\\quintiles.net\enterprise\Apps\sasdata\SASa\sas\Sunovion\S 363856\BZA44200\Biostatistics\Documentation\SAP\V1\SEF	SEP- 2 361-301 SAP Final V	/1.0_26JUL2023

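### The synopsis ties stopping of other psychotropics to the baseline PET, while Section 10.3.1, exclusion 25 and the SAP count from first dose, so co-medication may differ between the two scans

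*Protocol*

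**What the plan says.** The rule for non-exempt psychotropics appears in four places, with two reference points.

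- **Protocol synopsis, Prior Medications.** These drugs "must be discontinued, as tolerated and clinically appropriate, prior to PET scan at screening in a manner that is consistent with labeling recommendations". No washout length is given.
- **Protocol Section 10.3.1.** They "are prohibited during the study and must be discontinued, as tolerated and clinically appropriate", with the time limit "for at least 5 half-lives or 14 days, whichever is longer), prior to the first dose of study drug". For this class the PET is not mentioned. The same section does set a PET-based deadline for clozapine (120 days).
- **Protocol Section 8.2, exclusion 25.** Disallowed drugs are counted "for at least 5 half-lives or 14 days prior to dosing, whichever is longer".
- **SAP Section 12.** It repeats the dosing-based count and adds: "Medications that stopped prior to the first dose of study drug will not be considered concomitant but prior medications".

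The baseline scan has a wide window: "The PET scan will be performed prior to dosing (Day -44 to Day -2". Section 7.1 makes screening part of the study: "The study will consist of 3 periods: Screening (up to 49 days), Treatment (2 weeks), and a Follow-up visit". Section 11.4 asks that conditions match at the two scans. It names time of day and head motion but not co-medication.

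The exemption is also unclear. Section 10.3.1 points to Section 10.3.4 for the exempt drugs, but the anxiolytics, hypnotics and drugs for extrapyramidal symptoms are listed in Section 10.3.3.

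**The concern.** The primary endpoint is a within-subject change between two scans with no control arm. Whatever differs systematically between the scans, other than study drug, is absorbed into that change. If a subject takes a non-exempt psychotropic at or just before the baseline PET and is long off it by Day 14, stopping that drug and starting study drug cannot be told apart in that subject.

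The planned tables would not show this. Under SAP Section 12, a drug taken up to the baseline scan and one stopped weeks before it are both prior medications if each ended before first dose. The PET population in Protocol Section 15.2 requires only a dose and two scans, and SAP Section 4.2 drops the Per Protocol population for the imaging analysis as well. The medication listing and the recorded scan dates would allow the two cases to be separated, but the SAP supplied plans no such step.

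**Working it through.** **Inputs.** Scan window Day -44 to Day -2 (Protocol synopsis and Section 7.1). Minimum washout W, the longer of 5 half-lives and 14 days, counted back from Day 1 (Section 10.3.1). No Day 0 (SAP Section 7.1). SD 0.00056/min, n = 16, effect 0.0005/min, alpha 0.05 (Protocol Section 15.1).

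**The plan's own figure.** Taking 0.00056 as the SD of the change, the noncentrality is 0.0005 / (0.00056/√16) = 3.57. The exact two-sided paired t-test has 91.5% power, which reproduces the stated figure of more than 90%. The interval widths below use the same reading.

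**Window.** 44 - 2 + 1 = 43 permitted scan days.

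**Following the first-dose rule only.** With W full drug-free days before Day 1, the latest last dose is Day -(W+1). Scan days on which the subject may still be taking the drug run from Day -44 to that day, so their number is 44 - W (for W from 14 to 44).

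| Washout W | Latest last dose | Scan days still on drug |
|---|---|---|
| 14 days | Day -15 | 44 - 14 = 30 of 43 |
| 20 days (assumed half-life 4 days) | Day -21 | 44 - 20 = 24 of 43 |
| 44 days (assumed half-life 8.8 days) | Day -45 | 44 - 44 = 0 of 43 |

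If the last dose under a 14-day rule is instead taken as Day -14, the first row becomes 31. These are calendar days in the least favourable compliant case. They are neither subjects nor probabilities.

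**Following both rules, W = 14.** The last dose must be before the scan day and no later than Day -15.

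- Scan on Day -44 to Day -14 (31 days): the last dose may be the day before, so the gap is 1 day.
- Scan on Day -13 to Day -2 (12 days): the last dose is Day -15 at the latest, so the smallest gap is 15 - 13 = 2 days to 15 - 2 = 13 days.
- Scan days while still taking the drug: 0 of 43.
- Gap at Day 14 after a last dose on Day -15: 14 days to Day -1, plus 1 to Day 1, plus 13 to Day 14, which is 28 days. It is longer if the drug stopped earlier.

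**Effect on the mean.** If k of n subjects had baseline uptake shifted by s, the mean change would move by k × s / n. The documents give neither k nor s, so no value is entered.

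**Cost of a sensitivity line.** 95% half-width = t(0.975, n-1) × 0.00056/√n.

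- n = 16: 0.000298/min
- n = 15: 0.000310/min (+4%)
- n = 14: 0.000323/min (+8%)

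If 0.00056 is a per-scan SD, each half-width is multiplied by √2 = 1.414 and the percentages are unchanged. The number excluded is an assumption.

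**The case against.** The strongest reply is that the rules do not conflict. The synopsis is current protocol text and requires stopping before the scan. Section 10.3.1 bars these drugs during the study, and screening is a study period. A site that reads the whole protocol stops before the PET and also meets the first-dose washout, and Section 11.4 already asks for matching conditions. Much of this stands. Section 10.3.1 is ambiguous, not permissive, and with both rules applied nobody is scanned while taking the drug. What remains is that the PET-based rule has no duration, so a 1-day gap complies. The synopsis also sends readers to Section 10.3 for detail, where the only timing for this class runs from first dose. For ECT, by contrast, Section 10.3.2 names screening explicitly: "Electroconvulsive therapy (ECT) is prohibited within 3 months prior to screening and during the study".

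A second reply is that no passage shows that any non-exempt psychotropic changes 18F-DOPA uptake, and that the PET analysis belongs to a separate SAP. Both are correct, which is why no bias is estimated and the analysis request is conditional. Disallowed medication is also reviewed as a possible important deviation (Protocol Section 15.3.3, SAP Section 9.1). Whether a drug taken at the baseline scan counts as disallowed, however, depends on which rule the reviewer applies.

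A reader might infer more than the documents support:

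- That Section 10.3.1 has no PET-based deadline at all. It has one, for clozapine.
- That 30 of 43 is the chance of a contaminated baseline. It assumes that the synopsis is ignored, the 14-day minimum applies and stopping is as late as allowed.

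**Conclusion.** The inconsistency is real and its severity is minor to moderate. For psychotropics other than clozapine and the background antipsychotic, one passage counts from the baseline PET without a duration, and three count from dosing without mentioning the PET. On-drug scan days range from 30 of 43 (first-dose rule alone, 14-day washout) to 0 (both rules, or a washout of 44 days or more). Even with both rules met, the gap can be 1 day at baseline against about 28 days or more at Day 14.

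Confidence is high for the textual inconsistency only. It does not extend to any realised bias. The documents do not say how many subjects, if any, were affected, or in which direction, so a reader should not conclude that the primary result is biased.

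**What to change.** 1. **Wording.** Reconcile the synopsis (Prior Medications), Protocol Section 10.3.1, exclusion 25 and SAP Section 12, so that the rule for other psychotropics and its timing relative to both the baseline PET and the first dose are consistent. Reconcile the exemption reference in Section 10.3.1 with the lists in Sections 10.3.3 and 10.3.4. Which rule and which exemptions apply is for the sponsor and the investigator; this review does not choose.
2. **Analysis.** Unless the separate PET SAP, which was not available, already does so, use the recorded medication dates (Section 10.3) and scan dates (Section 11.4) to identify subjects with a non-exempt psychotropic present, or recently stopped, at one PET and not the other. Define recently stopped before the scans are analysed. Report the primary mean change and 95% CI with and without these subjects. The exemption lists must be settled first, because they define the set.

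The cost is a text clarification and one sensitivity line from data already collected. The downside is the somewhat wider interval in that line. If enrolment is over, the wording can no longer affect conduct, but the sensitivity line remains possible.

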### **10.3.2. Prohibited Therapies**

Electroconvulsive therapy (ECT) is prohibited within 3 months prior to screening and during the study.

### **10.3.3. Restricted Medications**

Caution should be taken with concomitant use of CYP2D6 substrates with SEP-363856 as SEP-363856 is a weak inhibitor of CYP2D6 (see to [Section 25](#)).

#### Concomitant Non-psychotropic Medications:

Non-psychotropic medications used to treat mild, chronic medical conditions may be used during screening and after enrollment if the dose and regimen have been stable ( $\pm 25\%$ ) for at least 30 days prior to screening. The concomitant medication dose may change, as needed, after enrollment (or be discontinued).  $\beta$ -adrenergic antagonists used to treat stable hypertension may be continued through the screening phase and post-initiation. Medications for short-term treatment of a medical condition (no more than 10 days) are allowed during the study with consultation with the Medical Monitor.

#### Concomitant Psychotropic Medications:

Treatment with benztrapine up to 6 mg/day will be permitted, as needed, for movement disorders. In cases where benztrapine is not available or a subject has had an inadequate response or intolerance to benztrapine treatment, the following medications may be used to treat acute extrapyramidal symptoms (EPS): biperiden (up to 16 mg/day) or trihexyphenidyl (up to 15 mg/day) or diphenhydramine (up to 100 mg/day) or procyclidine (up to 30 mg/day). Treatment with propranolol (up to 120 mg/day) will be permitted as needed for akathisia.

Concomitant use of lorazepam, temazepam, eszopiclone, zaleplon, zolpidem, and zolpidem CR is permitted at the discretion of the Investigator with the following restrictions:

1. lorazepam (or equivalent benzodiazepine) is permitted for clinically significant anxiety/agitation or as a sedative/hypnotic up to a maximum daily dose of 6 mg/day. Intramuscular lorazepam is permitted up to 4 mg/day for acute anxiety/agitation, as clinically indicated. Lorazepam should be used sparingly, when clinically required, per Investigator judgment.

2. temazepam ( $\leq$  30 mg/day), eszopiclone ( $\leq$  3 mg/day), zaleplon ( $\leq$  20 mg/day), zolpidem ( $\leq$  10 mg/day), and zolpidem CR ( $\leq$  12.5 mg/day) may be administered at bedtime for insomnia, as needed.
3. hypnotic agents should be administered no more than once nightly and should not be used in combination.

The date and time of the last dose taken prior to scheduled efficacy assessments must be recorded at each visit. Subjects should be encouraged to avoid taking sedative/hypnotic medications within 8 hours of scheduled efficacy assessments.

Medications used for the treatment of anxiety/agitation and insomnia (eg, lorazepam and zolpidem) should not be used in close temporal proximity (defined as administration within 2 hours of each other).

Similar drugs at equivalent dosages will be permitted as described in the Operations Manual or in consultation with the Medical Monitor.

